Probing Cortical Excitability and Cognitive Function With TMS

May 22nd, 2025

NCT03652012

Participants:

[figure not shown]
Forty community-dwelling older adults were enrolled in this study. All participants completed comprehensive neuropsychological assessments to determine cognitive status based on the revised Mayo Clinic criteria for mild cognitive impairment (MCI), which include: (a) a self- or informant-reported cognitive complaint; (b) objective evidence of cognitive impairment; (c) preserved independence in functional abilities; and (d) absence of dementia(Petersen et al., 2014).

Classification of MCI was further supported using the Jak/Bondi actuarial neuropsychological method and the National Alzheimer's Coordinating Center (NACC) Uniform Data Set Version 3.0 Neuropsychological Battery(Weintraub et al., 2018). Participants were classified as cognitively impaired if they scored more than 1 standard deviation below age- and education-adjusted normative data on either: (i) two tasks within the same cognitive domain, or (ii) one task in each of three different domains, consistent with the Jak/Bondi criteria(Jak et al., 2009; Jak et al., 2016).

Based on these criteria, 20 participants were classified as having MCI, while the remaining 20 were demographically matched and served as cognitively normal controls.

Trial Design:

Each participant attended two study visits (Fig. 1). During session 1, participants completed a comprehensive neuropsychological battery. The groups were counterbalanced to include 20 classified as cognitively normal (CN) and 20 classified as MCI.

Session 2 comprised both Magnetic Resonance Imaging (MRI) and Transcranial Magnetic Stimulation (TMS). We acquired functional MRI (fMRI) data both before and immediately upon completion of the TMS protocols. We evaluated resting-state functional connectivity between the stimulation site (M1) and neighboring regions (e.g., somatosensory cortex; S1).

TMS was applied to the primary motor cortex using an infrared-based frameless stereotactic neuronavigation system (Polaris System, Localite Version 3.0.41). Single-pulse protocols were

used to assess the features of cortical excitability, as described in the outcome measures below(Chou et al., 2022). To identify the stimulation target corresponding with the APB muscle, the motor ‘hand knob’ area was visually identified on the left pre-central gyrus for each participant’s anatomical MRI. The stimulation target was subsequently refined based on observed motor responses from the APB. The optimal motor hotspot was recorded within the neuronavigation system, which enabled precise coil positioning throughout the TMS session.

We utilized electromyography to record M1-TMS measures of cortical excitability, described below. Electromyography data were collected from the abductor pollicis brevis (APB) muscle, which was identified via manual palpation. Three electrodes were placed in a belly–tendon montage, with the grounding electrode placed on the ulnar tuberosity. The EMG data captured motor evoked potentials (MEPs), from the APB muscle activity induced by single pulses of TMS. There were two different experimental conditions for the M1-TMS stimulus-response curve, with half of the participants in each cohort assigned to each condition.

[figure not shown]
In addition to single-pulse measures of cortical excitability, intermittent theta-burst stimulation (iTBS) was applied to the same stimulation target. The iTBS protocol comprised 600 pulses at 80% of the active MT. The stimuli were patterned in three-pulse bursts at 50 Hz, which repeated at a frequency of 5 Hz, and were delivered in intermittent trains, each lasting 2s with a 6.9-s inter-train interval for a total duration of 178s.

Outcome Measures:

This study comprised several M1-TMS measures of cortical excitability; these included resting motor threshold (rMT), the stimulus-response curve, and the cortical silent period.

rMT is the minimum TMS intensity necessary to elicit a twitch in a targeted muscle at rest, which is operationally defined as an MEP $\geq 50\mu\text{V}$ in at least 50% of trials. A decrease in resting motor threshold (rMT) indicates that less energy is required to transsynaptically depolarize pyramidal tract neurons, signifying heightened cortical excitability(Ziemann et al., 2015).

[figure not shown]
The **stimulus-response curve** is evaluated by examining how MEP amplitude—typically measured as peak-to-peak response—varies across different stimulus intensities(Devanne et al., 1997). This relationship follows a sigmoidal trajectory, often called the stimulus-response, recruitment, or input-output curve. The curve is typically modeled using a sigmoidal function, such as Boltzmann’s

equation, by plotting stimulus intensity against corresponding MEP amplitudes. Among the various parameters that can be derived from this function, our analysis focused on the slope of the curve's linear region, which reflects corticospinal excitability (Fig. 2). This outcome measure was collected under two experimental conditions: with a tonic voluntary muscle contraction (20% of max voluntary contraction) or with the corresponding muscle at rest. Half of the participants from each cohort were assigned to each experimental condition.

The **CSP** is the temporary disruption of background voluntary muscle activity immediately following the MEP, resembling electrical silence in the EMG signal (Fig 3). Quantified as the duration of EMG absence following an MEP, CSP is a measure of GABA-mediated intracortical inhibition (Paulus et al., 2008).

Lastly, we assessed the resting-state functional connectivity of the stimulation site (M1). We assessed group differences at baseline as well as group differences in the iTBS-induced change in functional connectivity.

Statistical Design and Analysis

This cross-sectional study examined group differences across the outcome measures described above. Two-sample t-tests compared the MCI and cognitively normal control groups on resting motor threshold (rMT), cortical silent period (CSP), and resting-state functional connectivity. We conducted a two-way factorial ANOVA with Group (MCI vs. control) and Condition (active vs. rest) as between-subject factors for the stimulus-response curve, which included an additional experimental condition. Our primary parameter of interest was the slope of the sigmoidal input-output curve, which reflects corticospinal excitability. We applied a Bonferroni-adjusted significance threshold to account for multiple comparisons across the stimulus-response parameters.

References

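### The connectivity outcome does not say how many M1-region pairs were compared; if more than one was, the t-tests carry no adjustment across pairs

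*Combined protocol and SAP*

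**What the plan says.** The combined protocol and SAP describes connectivity in three places.

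- Trial Design: "We evaluated resting-state functional connectivity between the stimulation site (M1) and neighboring regions (e.g., somatosensory cortex; S1". The set of regions is plural and open, and S1 is given as an example.
- Outcome Measures, last paragraph: "Lastly, we assessed the resting-state functional connectivity of the stimulation site (M1", with no partner region mentioned, followed by "We assessed group differences at baseline as well as group differences in the iTBS-induced change in functional connectivity". Connectivity is therefore analysed twice, at baseline and as change.
- Statistical Design and Analysis: "Two-sample t-tests compared the MCI and cognitively normal control groups on resting motor threshold (rMT), cortical silent period (CSP), and resting-state functional connectivity".

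The same section states the only multiplicity control: "We applied a Bonferroni-adjusted significance threshold to account for multiple comparisons across the stimulus-response parameters". It also gives the parameter of main interest: "Our primary parameter of interest was the slope of the sigmoidal input-output curve, which reflects corticospinal excitability".

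The text has no list of regions, no pair named as deciding, no rule for combining regions into one value, and no significance level. The figures were not available for this check.

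**The concern.** A two-sample t-test needs one number per participant, and the plan does not say which number that is for connectivity. Three readings fit the text: one M1-region pair, one composite over regions, or a separate test for each pair. Under the third, the stated correction does not reach the connectivity tests, so each pair would be judged at the unadjusted level. Choosing a pair after looking at several has the same effect.

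This differs from multiplicity across outcomes. Calling connectivity secondary, or adjusting across rMT, CSP, slope and connectivity, would still leave an unspecified number of region tests under one label. A reader told that MCI and control groups differ in M1 connectivity could not tell whether this was the only test or the most favourable of several.

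**Working it through.** **Inputs from the document**

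- Group sizes (Participants): "20 participants were classified as having MCI, while the remaining 20 were demographically matched and served as cognitively normal controls". So n = 20 per group and 20 + 20 - 2 = 38 degrees of freedom.
- Two connectivity analyses, baseline and change (Outcome Measures).
- Two-sample t-test (Statistical Design and Analysis).

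**Assumptions, because the document is silent**

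- Two-sided 0.05 for each test.
- k region pairs tested, k from 1 to 10.
- A common correlation between region values, from 0 to 0.9.

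The plan gives no error rate, power or effect size for connectivity, so there is no figure of its own to reproduce.

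**Step 1: independent tests.** The chance of at least one false group difference in one analysis is 1 - (1 - 0.05)^k.

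- k = 1: 0.050
- k = 2: 1 - 0.95^2 = 0.0975
- k = 3: 1 - 0.95^3 = 0.143
- k = 6: 1 - 0.95^6 = 0.265
- k = 10: 1 - 0.95^10 = 0.401

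**Step 2: correlated regions.** Simulation of 40,000 null data sets per setting, 20 versus 20, pooled t-test, reject if any |t| exceeds the 0.975 quantile of t with 38 df:

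| k | corr. 0 | 0.3 | 0.5 | 0.7 | 0.9 |
|---|---|---|---|---|---|
| 1 | 0.051 | 0.050 | 0.050 | 0.049 | 0.050 |
| 2 | 0.097 | 0.096 | 0.091 | 0.082 | 0.069 |
| 3 | 0.142 | 0.134 | 0.126 | 0.107 | 0.086 |
| 4 | 0.182 | 0.173 | 0.158 | 0.135 | 0.094 |
| 6 | 0.267 | 0.240 | 0.214 | 0.167 | 0.110 |
| 10 | 0.401 | 0.353 | 0.291 | 0.215 | 0.131 |

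The zero-correlation column agrees with Step 1 within simulation error. Correlation shrinks the inflation but does not remove it over this range. The k = 1 row shows that one pair or one composite leaves the rate at 5%.

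**Step 3: effect of adjustment.** When no region differs, Holm's chance of any rejection equals Bonferroni's at 0.05/k. The simulated rate at that threshold, for k = 2 to 6 over the same correlations, lies between 0.022 and 0.051, so it is held at 5% within simulation error.

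**Step 4: cost in power.** The standardised difference d detectable with 80% power comes from the noncentral t with 38 df and noncentrality d × sqrt(20/2), at level 0.05/k (Holm's strictest step):

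- k = 1, level 0.05: d = 0.91
- k = 2, level 0.025: d = 1.01
- k = 3, level 0.0167: d = 1.06
- k = 6, level 0.0083: d = 1.15

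**The case against.** The strongest reply is that the plan never says each pair was tested. The statistical section lists connectivity beside rMT and CSP, each naturally one value per participant, and Outcome Measures speaks of the connectivity of M1 without naming partners. One M1 summary or one M1-S1 value fits this as well as a series of tests. That stands: a reader might infer that the plan commits to unadjusted tests of every pair, but the documents do not support this. What they show is an undefined endpoint, with inflation that depends on how it was analysed.

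A reader might also infer that the plural implies at least two tests, and hence a false-positive rate of at least 1.5 times 0.05. Neither step holds. Several regions can feed a single value, and with two tests at correlation 0.9 the rate is about 7%, below 7.5%. The documents give no correlation that would rule out such values.

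It is also tempting to make M1-S1 the deciding pair because it is the only one named. But S1 appears only as an example, and the document is written in the past tense throughout. Naming the pair now could be a choice made after the results and would not restore a prespecified 5% error.

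Finally, the consequence is limited. The slope is the parameter of main interest, and connectivity is introduced last among the outcomes. This too stands. None of it, however, tells the reader which connectivity value was tested, or extends the stated correction to connectivity.

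**Conclusion.** The point holds as a specification gap with conditional inflation. The region set is open, no deciding pair or composite is named, and the stated Bonferroni threshold does not cover connectivity. If more than one pair was tested, the chance of at least one false group difference within each connectivity analysis is about 7-10% for 2 regions and 11-26% for 6, over correlations of 0.9 to 0. If a single pre-chosen pair or a composite was used, it is 5%.

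These rates rest on an assumed two-sided 0.05 level, an assumed number of regions and assumed equal correlations; only the 20 per group comes from the plan. They apply to each of the two analyses separately. The conclusions at risk are those on connectivity only, not those on slope, rMT or CSP.

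**What to change.** In Statistical Design and Analysis:

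- State the significance level, list every M1-region pair tested, and report all of them.
- Apply Holm across the pairs, including M1-S1, once within the baseline analysis and once within the change analysis.
- Treat M1-S1 as the single deciding pair only if that choice was made before results were seen, and say when it was made. Otherwise label the connectivity findings exploratory.
- If one composite value per participant was used, say so and define it. No adjustment across regions is then needed.

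This controls error within each analysis, not over baseline and change together, and the text should say so.

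The cost is a few sentences and adjusted p-values from existing scans. The downside is a stricter threshold per region: at Holm's strictest step, the detectable difference rises from about 0.91 SD to 1.01 SD with 2 tests and 1.15 SD with 6.

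### Should the t-test on connectivity change have included the contraction-or-rest condition?

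*Combined protocol and SAP*

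**What the plan says.** The Trial Design section places the scans around the whole stimulation session: "We acquired functional MRI (fMRI) data both before and immediately upon completion of the TMS protocols". That session held single-pulse measures and, at the same target, intermittent theta-burst stimulation (iTBS). For the stimulus-response curve there were two conditions, contraction or rest, "with half of the participants in each cohort assigned to each condition".

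The Outcome Measures section lists two connectivity comparisons: "We assessed group differences at baseline as well as group differences in the iTBS-induced change in functional connectivity". Statistical Design and Analysis then assigns the test: "Two-sample t-tests compared the MCI and cognitively normal control groups on resting motor threshold (rMT), cortical silent period (CSP), and resting-state functional connectivity". No other test is named for connectivity, so I read it as covering both the baseline value and the change. The Group by Condition ANOVA is named only for the stimulus-response curve. The same section sets the priority among outcomes: "Our primary parameter of interest was the slope of the sigmoidal input-output curve".

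**The concern.** The interval between the two scans contains a procedure that differed by assignment between participants, at the cortical site whose connectivity is measured. The plan models that factor for the stimulus-response curve but not for connectivity change. Two things could go wrong when a factor of this kind is left out. If it were unevenly spread over the groups, the group difference would be biased and the type I error could rise. If it were evenly spread but influential, the residual variance would grow and power would fall. With 20 per group there is little power to spare.

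The point can apply only to the change. The baseline scan precedes the TMS session, so Condition cannot have affected it.

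**Working it through.** The document gives no power, effect size, SD or numeric alpha, so there is no figure of the plan's own to reproduce.

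**Inputs from the document.** 40 participants, 20 with MCI and 20 controls (Participants); half of each group in each condition (Trial Design and Outcome Measures), hence 10 per cell.

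**Assumptions.** Two-sided alpha 0.05; within-cell SD of connectivity change = 1; group difference *d*; Condition shift *c*, both in SD units.

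**Step 1: bias.** In each group, 10/20 = 0.5 of participants contracted. Condition adds 0.5*c* to both group means, so its contribution to the difference is 0.5*c* − 0.5*c* = 0. This follows from the equal split alone and does not depend on how participants were assigned to a condition. If Condition acted differently in the two groups, the t-test would still estimate the group difference averaged over equal halves.

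**Step 2: variance.** The true variance of the group difference is 1/20 + 1/20 = 0.1, whatever *c* is. The pooled variance estimate absorbs the omitted shift: each participant lies *c*/2 from the group mean, which adds 40 × *c*²/4 = 10*c*² to the residual sum of squares on 38 df. Its expectation is 1 + (*c*²/4)(40/38):

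- *c* = 0.25: 1.016
- *c* = 0.5: 1.066
- *c* = 1.0: 1.263

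The standard error is overstated, so the test errs towards non-significance.

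**Step 3: type I error and power.** The group difference is normal with mean *d* and variance 0.1; the residual sum of squares is noncentral chi-square with 38 df and noncentrality 10*c*². Integrating over it gives, for the t-test:

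| Shift *c* (SD) | Type I error | Power, *d* = 0.5 | Power, *d* = 0.8 | Power, *d* = 1.0 |
|---|---|---|---|---|
| 0 | 0.0500 | 0.338 | 0.6934 | 0.869 |
| 0.25 | 0.0482 | 0.332 | 0.6877 | 0.865 |
| 0.5 | 0.0433 | 0.315 | 0.6705 | 0.855 |
| 1.0 | 0.0284 | 0.255 | 0.6029 | 0.809 |

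With Condition as a second main effect (37 df), power at *d* = 0.8 is 0.6928 whatever *c* is. The differences are:

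- *c* = 0: 0.6934 − 0.6928 = 0.0006, in favour of the t-test
- *c* = 0.25: 0.6928 − 0.6877 = 0.0051, in favour of adjustment
- *c* = 0.5: 0.6928 − 0.6705 = 0.0223, in favour of adjustment
- *c* = 1.0: 0.6928 − 0.6029 = 0.0899, in favour of adjustment

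The two tests break even at *c* = 0.082. The loss from omitting Condition reaches 1 point at 0.340 SD and 5 points at 0.745 SD. A separate simulation (100,000 runs per scenario, *d* = 0.9) agrees: t-test power is 0.790, 0.771 and 0.715 at *c* = 0, 0.5 and 1.0, against about 0.79 with Condition included.

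**Step 4: is a large shift suggested anywhere?** No. The contrast is the muscle state during one single-pulse block. The other parts of the session are described alike for everyone. The silent period is a "temporary disruption of background voluntary muscle activity immediately following the MEP", so it requires contraction, and the stimulation dose is given once for all: "The iTBS protocol comprised 600 pulses at 80% of the active MT". If the silent period was recorded in all participants, those in the rest condition contracted as well, which weakens the contrast further.

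**The case for a change.** The best case for adjusting is the lopsided payoff. Condition is an assigned factor already coded for the ANOVA. Including it costs 0.0006 of power at *d* = 0.8 if it does nothing, and returns about 2 points at a 0.5 SD shift and 9 points at 1.0 SD. The arithmetic is correct, and had the analysis been still to come, including the factor would have been a reasonable choice.

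Two things limit it. The gain depends wholly on an effect that the document neither gives nor implies, and that may be zero. The t-tests are also reported in the past tense. An adjusted model added now would stand beside the planned result as a post-hoc analysis. The planned test would gain no power, and there would be a second p-value for connectivity, while the stated Bonferroni rule covers only the stimulus-response parameters.

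A second argument is protection against uneven scan loss, since the text available gives no exclusion rule. With cells of 10/8 against 8/10 the group difference moves by (10/18 − 8/18)*c* = 0.11*c*, and type I error is still 4.9, 4.6 and 3.7% at shifts of 0.25, 0.5 and 1.0 SD. With 10/7 against 7/10 it stays at or below 5.0%. Only a loss of four scans per group in opposite conditions (10/6 against 6/10) pushes it up, to about 5.6, 7.0 and 7.9% at 0.5, 1.0 and 1.5 SD. This part stands as a condition: the t-test's validity depends on the equal split surviving, at least roughly, to the analysis. No lost scans are reported, so it is not a fault of the plan.

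Third, the plan attributes the change to iTBS although the interval holds other stimulation too. That concerns what the change is attributed to. A Condition term would not settle it, and it does not make the group comparison invalid.

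**Conclusion.** The concern does not hold. With 10 participants per cell, Condition cancels from the group difference in connectivity change, and the two-sample t-test is unbiased and at worst conservative. At an assumed *d* = 0.8 the price of omitting Condition is nothing if it has no effect, 2.2 points of power at a 0.5 SD shift, and 5 points only at about 0.75 SD. The document supports no such shift, the outcome is not the primary parameter, and no stated conclusion depends on the choice.

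This rests on the equal split holding in the analysed scans, on the assumed effect sizes, unit SD and 0.05 level, and on reading the scan timing as bracketing the stimulus-response block. The order of measures within the session is not stated in the text available, and the figure showing the visits is not reproduced. If the block lay outside the scan interval, the question would not arise.

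### Does analysing contracted-muscle and resting-muscle slopes in one ANOVA call for a log-scale primary analysis?

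*Combined protocol and SAP*

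**What the plan says.** Under Outcome Measures, the curve is described as usually being obtained by fitting a sigmoid "by plotting stimulus intensity against corresponding MEP amplitudes". It was measured either "with a tonic voluntary muscle contraction (20% of max voluntary contraction) or with the corresponding muscle at rest", and "Half of the participants from each cohort were assigned to each experimental condition". Under Statistical Design and Analysis, "Our primary parameter of interest was the slope of the sigmoidal input-output curve". The model is given there as: "We conducted a two-way factorial ANOVA with Group (MCI vs. control) and Condition (active vs. rest) as between-subject factors for the stimulus-response curve". A multiplicity provision follows: "We applied a Bonferroni-adjusted significance threshold to account for multiple comparisons across the stimulus-response parameters".

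The text does not state the scale of the slope entering the ANOVA, any normalisation, an assumption check, a method for unequal variances, or how an interaction would be read. It specifies no comparison of groups within a single condition.

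**The concern.** A slope in amplitude units is positive, and quantities of that kind often have a spread that grows with their mean. The two muscle states may well produce slopes of different size. If they do, and the slopes go into the ANOVA untransformed, three things follow:

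- The contraction cells supply most of the pooled error variance and most of the Group contrast, so the resting half of the sample counts for little.
- A group effect that is the same percentage in both states becomes a Group by Condition interaction.
- If someone compared groups within one condition using the pooled error, the test would be too liberal under contraction and too conservative at rest.

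This is the parameter the plan names as its main interest, so the reading of the main result would be at stake. The obvious remedy is to make the logarithm of the slope the primary outcome and report geometric mean ratios.

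**Working it through.** **Inputs from the documents.** "Forty community-dwelling older adults were enrolled in this study" (Participants); "The groups were counterbalanced to include 20 classified as cognitively normal (CN) and 20 classified as MCI" (Trial Design); half of each cohort per condition. Hence 40 / (2 × 2) = 10 per cell and 4 × (10 − 1) = 36 error degrees of freedom. There is no planned power or effect size to reproduce.

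**Assumptions, none from the documents.** Log-normal slopes with the same CV in every cell (0.4 or 0.6, unless another value is given); contraction multiplies the mean slope by k; MCI multiplies it by g in both states; two-sided alpha 0.05, because the number of parameters in the Bonferroni correction is not given.

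**1. Algebra of a proportional effect.** Let m be the resting control mean. The cell means are m and gm at rest, km and kgm under contraction. The raw interaction contrast is (kgm − km) − (gm − m) = (k − 1)(g − 1)m, which is non-zero whenever k and g both differ from 1. With constant CV, the contraction cells' share of the pooled error variance is k²/(1 + k²): 4/5 = 80% at k = 2, 9/10 = 90% at k = 3. Their share of the Group contrast is k/(1 + k): 67% and 75%. With k = 1 there is no dominance.

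**2. Cost if those assumptions hold (simulation, g = 1.5).**

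| CV | k | Power for Group, raw | Power for Group, log | Interaction declared, raw | Interaction declared, log |
|---|---|---|---|---|---|
| 0.4 | 2 | 0.84 | 0.90 | 0.16 | 0.05 |
| 0.4 | 3 | 0.80 | 0.90 | 0.27 | 0.05 |
| 0.4 | 4 | 0.76 | 0.90 | 0.35 | 0.05 |
| 0.6 | 2 | 0.52 | 0.62 | 0.09 | 0.05 |
| 0.6 | 3 | 0.48 | 0.62 | 0.14 | 0.05 |
| 0.6 | 4 | 0.45 | 0.62 | 0.18 | 0.05 |

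The power loss runs from 0.90 − 0.84 = 0.06 to 0.62 − 0.45 = 0.17. At k = 1.5 it is smaller: 0.87 against 0.90 (CV 0.4) and 0.54 against 0.62 (CV 0.6), with an interaction declared in 9% and 6.5% of runs.

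**3. Error rate of the planned tests.** With equal cells, the variance of the Group contrast, taken as the sum of the MCI cell means minus the sum of the control cell means, is the sum of the four cell variances divided by 10. That is 4 times their average over 10, which is exactly what the pooled error estimates, so the F-test stays correctly scaled when variances differ. Only the effective degrees of freedom drop. For k = 3 and no group effect, the relative variances are 1, 1, 9, 9, giving 20² / [(1 + 1 + 81 + 81)/9] = 400/18.2, or about 22 instead of 36. That moves the two-sided 5% critical value only from 2.03 to 2.07. Simulated rejection with no group effect is 0.046 to 0.053 for Group and 0.045 to 0.055 for the interaction, for k from 1 to 5 and CV from 0.3 to 0.7.

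**4. The reverse case.** Suppose MCI adds the same absolute amount d in both states. The raw interaction is then zero and the log one is not. With k = 3 and d equal to half the mean control slope, d = 0.5 × (m + 3m)/2 = m. The group ratio is (1 + 1)/1 = 2 at rest and (3 + 1)/3 = 1.33 under contraction. Simulated with d set in this way for k = 2 to 4, the log-scale ANOVA declares an interaction in about 16% to 58% of runs (CV 0.4) or 10% to 32% (CV 0.6), against 5% on the raw scale.

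**The case for a change.** The best case for a change is that the algebra in step 1 needs no simulation. The text names amplitudes and no transformation, so the raw scale is the natural reading, and a reader could not tell a state-dependent group effect from an effect of scale. A log-slope analysis would cost little, and if the CV really is constant it also gains power.

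The algebra stands, and so does the observation that scale and variance handling are unstated. Three parts do not carry through.

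- **The premise.** The raw scale is inferred from silence and from a sentence about how such curves are generally fitted. Larger and more variable slopes under contraction are plausible, but nothing in the documents shows them.
- **The error-rate argument.** The distorted figures (11% to 15% under contraction, about 0.5% at rest) belong to pooled-error comparisons within a condition. The plan contains no such comparisons. An analyst who added them could use each condition's own variance.
- **The interaction argument.** If the effect is proportional, the absolute group difference really does differ between states, so a raw-scale interaction is a true statement on that scale and not a false positive. Nor is the model additive in the sense of leaving a term out: a factorial ANOVA ordinarily includes the interaction.

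**Conclusion.** No change is needed. The planned F-tests keep their size in this balanced design whatever the ratio of slopes between conditions, within the range examined (1 to 5). The loss of power for Group, about 0.06 to 0.17, depends wholly on assumed log-normality, constant CV, a ratio of 2 to 4 and a proportional 1.5-fold group effect; it shrinks at smaller ratios. Neither scale protects the interaction in general: raw favours an additive truth, log a proportional one, and the documents do not say which applies. Choosing between them is a matter on which competent statisticians differ. The document also reports the ANOVA in the past tense, so replacing the primary scale now would be a post hoc choice. The unstated scale is ordinary missing detail. An analyst can look at the residuals, state the scale used and show the other one alongside, without amending the plan.

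### Does the missing Bonferroni divisor, with no ANOVA effect named for the slope, leave the slope's test undefined?

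*Combined protocol and SAP*

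**What the plan says.** The document is a short combined protocol and SAP, written in the past tense.

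- **Aim.** Statistical Design and Analysis opens with: "This cross-sectional study examined group differences across the outcome measures described above".
- **Model.** For the curve: "We conducted a two-way factorial ANOVA with Group (MCI vs. control) and Condition (active vs. rest) as between-subject factors for the stimulus-response curve". The reason given for the second factor is that this outcome was collected under two conditions.
- **Parameter.** The same section says: "Our primary parameter of interest was the slope of the sigmoidal input-output curve". Outcome Measures says: "Among the various parameters that can be derived from this function, our analysis focused on the slope".
- **Multiplicity.** The section closes with: "We applied a Bonferroni-adjusted significance threshold to account for multiple comparisons across the stimulus-response parameters".
- **Numbers.** There are 20 MCI and 20 cognitively normal participants (Participants; Trial Design). Outcome Measures adds: "Half of the participants from each cohort were assigned to each experimental condition".

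The text does not list the parameters in the Bonferroni family, and it gives no divisor, base alpha, sidedness or adjusted threshold. It does not say in so many words which of the three ANOVA effects is the test of the slope.

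**The concern.** A two-way ANOVA gives three omnibus tests: Group, Condition and their interaction. If none is designated, one could be chosen after the results are known. A Bonferroni threshold cannot be reproduced without its divisor, and the slope is the only curve parameter named although the adjustment refers to several. One might therefore read the slope as singled out and tested unadjusted, or as one of k parameters tested at alpha/k. A Group p-value between those two cut-offs would then be positive or negative depending on a number the document does not give. With 10 participants per cell, the choice has a visible effect on power.

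**Working it through.** The plan states no threshold, power, effect size or SD, so there is no figure of its own to reproduce. The check has two parts: what the wording settles, and what the remaining gap is worth.

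**1. Which effect tests the slope.** The section's first sentence sets the aim as group differences on every listed outcome. rMT, CSP and connectivity are each compared between MCI and control by two-sample t-tests. The curve gets an ANOVA only because of its extra condition. The counterpart of those t-tests is the Group main effect. Nothing in the text points to Condition or the interaction as the main test.

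**2. What the slope is primary to.** The word primary is attached to the slope as a parameter, between the sentence on the curve's ANOVA and the sentence on the curve's parameters. No primary endpoint is named for the study, and the other outcomes stand alongside unranked. The natural reading is that the slope comes first among the curve parameters.

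**3. Whether the slope is inside the family.** The slope is a stimulus-response parameter, and the adjustment covers those parameters with no exception. Testing the slope unadjusted would need a rule that is not in the text.

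**4. What the unknown divisor is worth.**

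Inputs from the document: 20 per group, half of each group per condition, hence 10 per cell, 4 cells and 40 − 4 = 36 error df with complete data.

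Assumptions, not in the document: base alpha 0.05, two-sided; normal slopes with equal SD; divisors k = 1 to 4; true group differences of 0.5 and 0.8 SD.

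Formulas: threshold = 0.05/k. Standard error of the Group difference = SD × √(1/20 + 1/20) = 0.316 SD. Noncentrality = d/0.316, which is 1.58 at 0.5 SD and 2.53 at 0.8 SD. Power comes from the noncentral t with 36 df.

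| k | Threshold | Difference detectable with 80% power | Power at 0.5 SD | Power at 0.8 SD |
|---|---|---|---|---|
| 1 | 0.05 | 0.91 SD | 33.7% | 69.2% |
| 2 | 0.025 | 1.01 SD | 23.7% | 57.9% |
| 3 | 0.0167 | 1.07 SD | 19.1% | 51.4% |
| 4 | 0.0125 | 1.10 SD | 16.3% | 46.9% |

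The share of studies whose verdict differs between two divisors is the difference in power:

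- **Slope inside the family, k unknown, 0.8 SD:** k = 2 against 3, 57.9 − 51.4 = 6.5 points; 3 against 4, 51.4 − 46.9 = 4.5; 2 against 4, 57.9 − 46.9 = 11.0.
- **The same at 0.5 SD:** 23.7 − 19.1 = 4.6; 19.1 − 16.3 = 2.8; 23.7 − 16.3 = 7.4.
- **Slope unadjusted against k = 2, 3, 4:** about 11, 18 and 22 points at 0.8 SD; about 10, 15 and 17 to 18 at 0.5 SD.

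The larger figures all belong to the reading that step 3 finds weaker.

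**5. Whether the planned test is sound.** In simulations with 10 per cell, assumed log-normal slopes (CV 30–70%, active-to-rest ratio 1–5) and no MCI effect, testing at 0.05 rejected in 4.4–5.6% of datasets for Group and 4.7–5.5% for the interaction. The ANOVA holds its level. If 0.05 is the base alpha, any divisor above 1 only makes the slope's test stricter.

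**The case for a change.** The strongest case for acting is that a decision rule should be reproducible from the plan. Even if Group is accepted as the effect, the threshold cannot be derived, and no other section supplies it. If the slope is primary only among curve parameters, that places it more firmly in the family, so the missing divisor governs it all the more. Knowing the divisor would not be enough either, because base alpha and sidedness are also absent. If the family also counted the three ANOVA effects, say 3 parameters × 3 effects = 9 tests, the threshold would be 0.05/9 = 0.0056 and power at 0.8 SD would be 35%. If instead only parameters were counted, with k = 1, and all three effects were read at 0.05, the chance of at least one false positive would be 1 − 0.95³ = 14.3%, treating the tests as independent.

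The omission stands: the document does not give the threshold, and a borderline result could not be classified from it. What does not stand is the step from there to a faulty analysis. The 14.3% arises only if Condition and the interaction are taken as further claims about MCI, and the stated aim is group differences. The wide range of thresholds reflects assumed divisors, and the plan does not direct an analyst to any wrong value. The slope's measurement scale cannot be judged here because Fig. 2 is not reproduced in the text available.

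**Conclusion.** No change to the plan follows. This is missing detail that analysts fill sensibly. The wording points to Group as the effect of interest and places the slope inside the Bonferroni family, and the planned ANOVA gives a valid test at whatever threshold applies. The unresolved part is the size of the divisor, with base alpha and sidedness. For divisors of 2 to 4 it changes the verdict in at most about 11% of studies at a true difference of 0.8 SD and about 7% at 0.5 SD. This rests on an assumed two-sided 0.05, complete data with 10 per cell, and normal slopes of equal spread.

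The work is reported as done, so a family and threshold were presumably chosen. Stating them in the results, with the date they were fixed, is ordinary reporting. So is giving the exact Group p-value and 95% confidence interval, from which a reader can apply any divisor. None of this alters the analysis, its power or its error rate. Separate-variance intervals within conditions, or a log-slope model, would address comparisons the plan does not contain.
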